This is a non-randomized prospective registry study to collect clinical data in the real-life setting in Japan. Enrolled subjects will include those who have been implanted with BSC pacing or defibrillation devices as well as post MI subjects with preserved EF and no device treatment. Subjects will be assigned to one of the 3 following Subject Cohorts according to device implanted:

1. ICD: 117 to 270 subjects
2. CRT-D: 95 to 250 subjects
3. PM/CRT-P: 172 to 200 subjects

A fourth cohort of non-implanted subjects will also be enrolled:

4. Non-device 172 to 300 subjects
(ESC Guideline 2016 Indicated but not implanted)

8.3. *Justification for the Study Design*

The primary objective of this study is to collect clinical event data for selected patient cohorts who are at risk of ventricular tachy-arrhythmias and HF events. In order to obtain “real world” data, the study inclusion/exclusion criteria and follow-up schedule have been written generally enough to allow for study site specific SOC which should accurately capture the clinical data in a “standard” clinical setting. Additionally, by requiring study sites to follow their specific SOC, risk to the subject is minimized because the treatment received by the subject will be similar to the treatment the subject would receive if not participating in the study.

Requiring that all implanted devices be programmed per protocol and the respective BSC IFU, all devices must be intended to be connected to the Latitude system during study duration.

The determination of sample size is provided in Section 12.1.6.

9. Subject Selection

9.1. *Study Population and Eligibility*

Inclusion and exclusion criteria are listed in Sections 9.2 and 9.3 below.

Subjects who are enrolled but later determined to not fulfil all inclusion and exclusion criteria at the time of enrolment will be considered to have incurred a Clinical Investigation Plan (CIP) deviation. These subjects will be withdrawn from the study immediately and will not be included in the planned data analysis.

9.2. *Inclusion Criteria*

All inclusion criteria apply only at the time of enrolment into the study.

If a subject's medical conditions change after inclusion into the study so that one or several of the general inclusion criteria and inclusion criteria of the pertinent cohort are no longer met, the subject remains in the study.

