9.2.2. Inclusion Criteria for the ICD Cohort

Subjects enrolled in the ICD group must also meet all of the following inclusion criteria (in addition to the General Inclusion Criteria):

Table 9.2-2: Inclusion Criteria for the ICD Cohort

1. De novo ICD system implanted successfully 45 days prior enrollment in subjects with symptomatic HF (NYHA Class II–III), and an LVEF $\leq 35\%$
2. Subjects are on OMT ≥ 3 months
3. Provided that the subjects are expected to survive substantially longer than one year with good functional status
4. Subjects have ischemic heart disease or DCM (dilated cardiomyopathy)
5. Subject was implanted with a BSC MRI Conditional System
6. Subjects have 2 to 5 risk factors out of the following prior device implant:
 - LVEF $\leq 35\%$
 - NYHA Class III or IV
 - Left bundle branch block (LBBB) with QRS >130 ms or any QRS >150 ms
 - Renal dysfunction (blood urea nitrogen chronically [BUN] >26 mg/dL)
 - Diabetes type I and II
 - Chronic atrial fibrillation (permanent or persistent according to ESC Guideline 2016¹¹)
 - Prior MI
 - Age >70 years
 - Smoking today or during last 5 years
7. Clinical subject conditions allow programming of defibrillation therapy according to the principals of the MADIT RIT study programming
8. Subjects' devices are currently intended to be followed on Latitude system

Abbreviations: BSC = Boston Scientific; BUN = blood urea nitrogen; ESC = European Society of Cardiology; HF = heart failure; ICD = implantable cardioverter-defibrillator; LBBB = left bundle branch block; LVEF = left ventricular ejection fraction; MI = myocardial infarction; MRI = magnetic resonance imaging; NYHA = New York Heart Association; OMT = optimal medical therapy

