9.2.4. Inclusion Criteria for the PM/CRT-P Cohort

Subjects enrolled in the PM/CRT-P cohort must also meet all of the following inclusion criteria (in addition to the General Inclusion Criteria):

Table 9.2-4: Inclusion Criteria for the PM/CRT-P Cohort

1. Subjects with a PM or CRT-P implanted during last 45 days prior enrollment (only BSC PG devices)
2. Subjects who are estimated to require right ventricle (RV) pacing >40%
3. PM subjects with LVEF \leq 50%
4. Paced or intrinsic QRS >90 ms, and any determined NYHA Class (symptoms of HF) or any previous HF admission (HF admission comprises the following conditions: admission to hospital because of HF and/or IV therapy for HF and/or upgrade of the PM/CRT-P)
5. Subjects' devices are currently intended to be followed on Latitude system.

Abbreviations: BSC = Boston Scientific; CRT-P = cardiac resynchronization therapy-pacemaker; HF = heart failure; LVEF = left ventricular ejection fraction; NYHA = New York Heart Association; PM = pacemaker; RV = right ventricle

9.2.5. Inclusion Criteria for the Non-device Cohort (ESC Guideline 2016 Indicated but not implanted)

Subjects enrolled in the Non-device cohort (ESC Guideline 2016 indicated but not implanted) must also meet all of the following inclusion criteria (in addition to the General Inclusion Criteria):

Table 9.2-5: Inclusion Criteria for the Non-device Cohort (ESC Guideline 2016 Indicated but not implanted)

- Subjects with symptomatic HF (NYHA Class II-III), and an LVEF $\leq 35\%$
- Subjects are on OMT ≥ 3 months
- Subjects are expected to survive substantially longer than 1 year with good functional status
- Subjects have ischemic heart disease or DCM (dilated cardiomyopathy)

OR

- LBBB QRS (≥ 130 ms) morphology and with LVEF $\leq 35\%$ despite OMT or
- QRS duration ≥ 150 ms and non-LBBB QRS morphology and with LVEF $\leq 35\%$ despite OMT

AND

1. No present or past implant device ICD, CRT-D, PM, or CRT-P
2. 2 to 5 risk factors out of the following:
 - LVEF $\leq 35\%$
 - NYHA Class III or IV
 - LBBB with QRS > 130 ms or any QRS > 150 ms
 - Renal dysfunction (chronically BUN > 26 mg/dL / > 9.28 mmol/L)
 - Diabetes type I and II
 - Chronic atrial fibrillation (permanent or persistent according to ESC Guideline 2016¹¹)
 - Prior MI
 - Age > 70 years
 - Smoking today or during last 5 years.

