9.3.1. General Exclusion Criteria

Subjects who meet any one of the following criteria (Table 9.3-1) are not allowed to be included in this clinical study. The exclusion criteria apply only at the time of enrolment into the study.

Table 9.3-1: General Exclusion Criteria

1. Subject is enrolled in any other concurrent study without prior written approval from BSC, with the exception of local mandatory governmental registries and observational studies/registries that are not in conflict and do not affect the following:
 - Schedule of procedures for the HINODE Study (i.e. should not cause additional or missed visits)
 - HINODE Study outcome
 - Conduct of the HINODE Study per Good Clinical Practice (GCP)/ International Standard Organization (ISO) 14155:2011/local regulations as applicable
2. Device implant revision is scheduled due to unstable result of an implant <45 days prior enrolment
3. Subjects with more than 5 of the following risk factors: LVEF \leq 35%, NYHA Class III or IV, LBBB with QRS 130 ms or QRS $>$ 150 ms, renal dysfunction (chronically BUN $>$ 26 mg/dL / $>$ 9.28 mmol/L), diabetes type I and II, chronic atrial fibrillation (permanent or persistent according to ESC Guideline 2016¹¹), prior MI, age $>$ 70 years, smoking today or during last 5 years
4. Subjects with chronic renal disease with chronic BUN \geq 50mg/dL or creatinine \geq 2.5 mg/dL
5. Subjects with coronary artery bypass graft (CABG) surgery or percutaneous coronary intervention (PCI) within the past three calendar months prior to enrollment
6. Subjects with enzyme-positive myocardial infarction within the past three calendar months prior to enrollment
7. Subjects who are expected to survive for <1 year with good functional status
8. Subject's physician does not allow participation
9. Subject is not willing and capable of participating in all testing or visits associated with this clinical study at an approved clinical study center and at the intervals defined by this CIP
10. Unwilling to sign the consent for participation
11. Women of childbearing potential who are or might be pregnant at the time of study enrolment
12. ICD and CRT-D cohorts: implanted with a non-BSC device system. PM/CRT-P cohorts: implanted with a non-BSC PG device.

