10.1. Point of Enrolment

Subjects will only be enrolled in this registry study if they meet all eligibility criteria and provide written informed consent. If a subject is found not to meet all applicable eligibility criteria, the subject will be withdrawn from the study; any points of ineligibility must be clearly documented in the enrolment/screening log. These subjects will be considered

consent ineligible as discussed in Section 10.3, and will not count towards the enrolment ceiling. Any subject that signs consent and meets all inclusion criteria and does not meet any Exclusion Criteria will be enrolled in the study. Any reportable events, as defined in Section 20 of this CIP, must be collected after written informed consent is obtained.

Subjects enrolled under protocol version C deviating from eligibility criteria of protocol version D will be withdrawn from the study. Other subjects previously not meeting eligibility criteria of protocol version C, but now meeting eligibility criteria of protocol version D, will be accepted under protocol version D and no protocol deviation will need to be documented in the eCRF.

10.2. *Withdrawal*

All subjects enrolled in this registry study (including those withdrawn from the clinical study or lost to follow-up) shall be accounted for and documented. If a subject withdraws from the study, the reason(s) shall be reported. If such withdrawal is due to problems related to investigational device safety or performance, the investigator shall ask for the subject's permission to follow his/her status/condition outside of the clinical study.

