12.2. General Statistical Methods

12.2.1. Analysis Sets

All subjects actively enrolled in the study (i.e. who meet all eligibility criteria at the time of enrolment into the study and who have given written informed consent) will be included in the primary endpoints analyses.

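### Enrolled subjects later judged ineligible leave the primary analysis with no deadline or outcome blinding, and one criterion is a forecast of one-year survival, which leaves the 12-month mortality endpoints of two cohorts open to hindsight removals

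*Combined protocol and SAP*

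**What the plan says.** **Removal rule.** Section 9.1 covers "Subjects who are enrolled but later determined to not fulfil all inclusion and exclusion criteria at the time of enrolment". It classes them as protocol deviations and adds: "These subjects will be withdrawn from the study immediately and will not be included in the planned data analysis". Sections 9.2 and 9.3 likewise end the study for a subject whose violation comes to light after enrolment.

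**Analysis set.** Section 12.2.1 defines the primary set as "All subjects actively enrolled in the study (i.e. who meet all eligibility criteria at the time of enrolment into the study", together with written consent. Section 10.3 defines an actively enrolled subject in the same way, and states that consent-ineligible subjects have no follow-up or adverse event reporting requirements.

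**The survival criterion.** General exclusion 7 (9.3.1), which applies to every cohort, is "Subjects who are expected to survive for <1 year with good functional status". The Non-device cohort also has an inclusion item in the heart failure branch of its either/or criteria (9.2.5): "Subjects are expected to survive substantially longer than 1 year with good functional status". The ICD cohort has a similar item (9.2.2): "Provided that the subjects are expected to survive substantially longer than one year with good functional status".

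**The endpoint.** All-cause mortality through 12 months is primary for PM/CRT-P (12.1.3) and Non-device (12.1.4), each tested against an 80% survival goal.

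**Limits on the rule.** Section 9.2 states: "All inclusion criteria apply only at the time of enrolment into the study". Section 9.3 says the same of exclusion criteria. A subject whose condition changes later stays in.

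**Related text.** Section 10.1 adds: "Subjects enrolled under protocol version C deviating from eligibility criteria of protocol version D will be withdrawn from the study". Section 10.2 allows data gathered before a withdrawal to be used. Section 22.3 provides central review of ECG criteria only.

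**The concern.** The rule lets the membership of the primary analysis set be decided after outcomes have occurred. For a measured criterion such as LVEF or age, that is a modest risk, because the baseline value is on file. Expected survival is different. It is an opinion, no measurement settles it, and it predicts the very event being counted. Once a subject has died at month four, it is easy to conclude that the enrolment forecast was mistaken.

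Nothing in the protocol prevents this. It sets no cut-off date for an ineligibility finding, names no decision-maker for non-ECG criteria, does not require that the finding be made unaware of outcome, and plans no analysis that retains the removed subjects. Section 17.4 says that sponsor staff may or may not be blinded to results.

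If deaths were removed more often than survivors, the survival estimate would rise towards and past the goal. Each cohort is tested alone against a fixed goal, so there is no control group in which the same bias would cancel.

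**Working it through.** **Inputs.** From Table 12.1-1: goal 80%, expected survival 90%, one-sided alpha 0.025, power 90%, 137 subjects analysed, 172 enrolled to allow for 20% attrition. The share q of 12-month deaths later ruled ineligible is not in the documents. It is an assumption, shown from 0% to 30%.

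**Step 1: reproduce the plan's figure.** With n = 137, the exact binomial test needs the smallest s with P(X ≥ s | 137, 0.80) ≤ 0.025. This is s = 119, so at most 18 deaths. Type I error is 0.0245, and power at 90% survival is 0.910. Attrition: 137 / 0.80 = 171.25, rounded up to 172. The stated sizes reproduce.

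**Step 2: worst case, in which only deaths are removed.** Let deaths D ~ Bin(137, 0.20) and removals K ~ Bin(D, q), and repeat the exact test on 137 − K subjects. Apparent survival tends to 0.80 / (1 − 0.20q).

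| q | Apparent survival | Chance of meeting the goal, n = 137 | n = 172 |
|---|---|---|---|
| 0 | 80.0% | 2.4% | 1.6% |
| 10% | 81.6% | 5.2% | 6.2% |
| 20% | 83.3% | 13.3% | 16.1% |
| 30% | 85.1% | 27.7% | 34.7% |

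The planned analysis is a Kaplan-Meier estimate with a log-log bound. Without censoring, that bound gives similar values at n = 137: 1.4%, 4.9%, 12.4% and 26.3%.

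**Step 3: survivors removed as well.** Let a share r of survivors also be removed. Apparent survival tends to 0.80(1 − r) / [0.80(1 − r) + 0.20(1 − q)]. At n = 137:
- q = 10%: the chance falls from 5.2% to 3.3% (r = 5%) and 1.9% (r = 10%).
- q = 20%: it falls from 13.3% to about 9% (r = 5%) and about 6% (r = 10%).
- r = q: the expression returns 0.80, so there is no bias.

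**Step 4: removals needed near the boundary.** One-sided exact p-values against 80%:
- n = 137, 19 deaths: P(X ≥ 118 | 137) = 0.041, fail. Drop 1: P(X ≥ 118 | 136) = 0.027, still fail. Drop 2: P(X ≥ 118 | 135) = 0.017, pass.
- n = 172, 24 deaths: P(X ≥ 148 | 172) = 0.0259, fail. Drop 1: P(X ≥ 148 | 171) = 0.0170, pass.

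The log-log bound without censoring gives the same number of removals in both cases.

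**The case against.** The strongest reply is that the criteria are fixed at enrolment. Expected survival is a forecast made that day, and a later death does not show that the forecast was violated. To drop a death, someone would have to re-judge the forecast against the plain sense of 9.2 and 9.3. This stands. A reader might infer that the protocol tells sites to discard early deaths, and it does not. What is missing is a rule that prevents hindsight re-judgement.

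Removals would also leave a trace. Section 10.1 requires points of ineligibility to be logged, 10.2 requires every enrolled subject to be accounted for, and 20.7 requires a death form. That makes removals auditable but does not return the subjects to the analysis.

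Most criteria are measured, and ECG criteria are read centrally. Removals on those grounds would take out survivors too, which shrinks the effect as in step 3. An eligible-only set is also defensible in itself when the expected rates come from selected trial populations.

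Two further inferences go too far. One is that the survival criterion biases all four primary endpoints. In ICD and CRT-D the primary endpoint is treated arrhythmia or arrhythmia-related instability, to which life expectancy has no direct link, and mortality is secondary there. The other is that withdrawing version C subjects is driven by outcome. Section 10.1 turns on amended criteria and also admits subjects who failed version C but meet version D, and no link to events is shown. Those withdrawals simply lack the same safeguard.

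**Conclusion.** The point holds for the PM/CRT-P and Non-device mortality endpoints. PM/CRT-P is reached through general exclusion 7 alone; Non-device is reached through that exclusion and, in its heart failure branch, an inclusion item. A stated removal rule acts on the primary set of a single-arm test, with no deadline and no outcome blinding, and one removable criterion forecasts the endpoint.

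The size is unknown, because the documents give no basis for q. The 5.2%, 13% and 28% at 137 subjects are worst cases: true survival exactly at the goal, deaths removed independently, no survivors removed. A reader might take them as the expected error rate, and the documents do not support that. The boundary result needs no assumed q: one or two removals can turn a narrow failure into a success. That is enough to close the gap in advance. It is a cheap improvement and does not show that the analysis is biased.

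**What to change.** 1. In 9.1 and 12.2.1, state that no enrolled subject is removed from the primary analysis on expected survival.
2. Allow removal only for an objective fact dated at or before enrolment, decided by existing reviewers who do not know the follow-up outcome. The central ECG reading is one example. Align 9.2, 9.3 and 10.3 with this.
3. Apply the same rule to version C subjects withdrawn under 10.1.
4. Add a sensitivity analysis that retains all consented, enrolled subjects, using their data up to withdrawal.
5. Reconcile 9.1, which leaves these subjects out of the analysis, with 10.2, which allows their data before withdrawal to be used.

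The cost is protocol and SAP wording and one extra analysis. A few ineligible subjects may stay in the primary analysis. The sample sizes do not change: with nobody removed, 137 analysed still gives power 0.910 and type I error 0.0245. Keeping every violator in the primary analysis would go further, but it is more debatable and is not needed to close this gap.

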9.2.1. General Inclusion Criteria

Subjects who meet all of the following criteria (Table 9.2-1) may be given consideration for inclusion in this clinical investigation, provided no exclusion criterion (see Section 9.3) is met.

Table 9.2-1: General Inclusion Criteria

1. Subject is aged 20 or above2. Subject is willing and capable of providing informed consent3. Subject is willing and capable of participating in all visits associated with this study at an approved clinical study site and at the intervals defined by this CIP4. Measured Ejection fraction value obtained by echocardiography or equivalent method as SOC:
• Device cohorts: within the last 3 months prior to enrolment• Non-device cohort: latest available within the last 12 months prior to enrollment in case there was no documented HF decompensation, MI or revascularization, otherwise within the last 3 months prior to enrollment 
And 12 lead ECG recording available as SOC:
 
• Device cohorts: pre-implant ECG maximum 45 days before implant; post-implant ECG• Non-device cohort: latest available maximum 12 months prior to enrollment 
and subject agrees in the data being used for this study.

Abbreviations: CIP = Clinical Investigation Plan

9.2.2. Inclusion Criteria for the ICD Cohort

Subjects enrolled in the ICD group must also meet all of the following inclusion criteria (in addition to the General Inclusion Criteria):

Table 9.2-2: Inclusion Criteria for the ICD Cohort

1. De novo ICD system implanted successfully 45 days prior enrollment in subjects with symptomatic HF (NYHA Class II–III), and an LVEF $\leq 35\%$
2. Subjects are on OMT ≥ 3 months
3. Provided that the subjects are expected to survive substantially longer than one year with good functional status
4. Subjects have ischemic heart disease or DCM (dilated cardiomyopathy)
5. Subject was implanted with a BSC MRI Conditional System
6. Subjects have 2 to 5 risk factors out of the following prior device implant:
 - LVEF $\leq 35\%$
 - NYHA Class III or IV
 - Left bundle branch block (LBBB) with QRS >130 ms or any QRS >150 ms
 - Renal dysfunction (blood urea nitrogen chronically [BUN] >26 mg/dL)
 - Diabetes type I and II
 - Chronic atrial fibrillation (permanent or persistent according to ESC Guideline 2016¹¹)
 - Prior MI
 - Age >70 years
 - Smoking today or during last 5 years
7. Clinical subject conditions allow programming of defibrillation therapy according to the principals of the MADIT RIT study programming
8. Subjects' devices are currently intended to be followed on Latitude system

Abbreviations: BSC = Boston Scientific; BUN = blood urea nitrogen; ESC = European Society of Cardiology; HF = heart failure; ICD = implantable cardioverter-defibrillator; LBBB = left bundle branch block; LVEF = left ventricular ejection fraction; MI = myocardial infarction; MRI = magnetic resonance imaging; NYHA = New York Heart Association; OMT = optimal medical therapy

9.2.3. Inclusion Criteria for the CRT-D Cohort

Subjects enrolled in the CRT-D Cohort of the study must also meet all of the following inclusion criteria (in addition to the General Inclusion Criteria):

Table 9.2-3: Inclusion Criteria for the CRT-D Cohort

 1. De novo CRT-D (BSC device system with IS4 connector and MRI conditionally safe) implanted successfully during last 45 days prior enrollment in symptomatic subjects with HF 2. A: Sinus rhythm and one of the following conditions: 
 • QRS duration \geq150 ms and LBBB QRS morphology and with LVEF \leq35% despite optimal medical therapy (OMT) • QRS duration \geq150 ms and non-LBBB QRS morphology and LVEF \leq35% despite OMT • QRS duration of 130 to 149 ms and LBBB QRS morphology and with LVEF \leq35% despite OMT
or

 3. Subjects have 2 to 5 risk factors out of the following prior to device implant: 
 • LVEF \leq35% • NYHA Class III or IV • LBBB with QRS $>$130 ms or any QRS $>$150 ms • Renal dysfunction (chronically BUN $>$26 mg/dL / $>$9.28 mmol/L) • Diabetes type I and II • Chronic atrial fibrillation (permanent or persistent according to ESC Guideline 2016¹¹) • Prior MI • Age $>$70 years • Smoking today or during last 5 years 4. ICD Defibrillation therapy will be programmed following MADIT RIT study programming principles (e.g. cut off rate \geq200 bpm or 170 bpm with 60 seconds delayed therapy programming) 5. Subjects devices are currently intended to be followed on Latitude system.

Abbreviations: BSC = Boston Scientific; BUN = blood urea nitrogen; CRT-D = cardiac resynchronization therapy-defibrillator; ESC = European Society of Cardiology; HF = heart failure; LBBB = left bundle branch block; LVEF = left ventricular ejection fraction; MI = myocardial infarction; MRI = magnetic resonance imaging; NYHA = New York Heart Association; OMT = optimal medical therapy

